9.7.1.8 Subject Characteristics

Subject characteristics included, but were not limited to: age, sex, race, country of origin, height, approximate and actual body weight, [REDACTED] GCS score at Baseline, [REDACTED].

Subject characteristics were obtained at screening or prior to discharge from the study and were summarized for all randomized subjects. If it was not possible to obtain all of the planned information at screening due to a subject's poor medical condition at enrollment, an attempt was made to obtain it prior to subject discharge. All recorded data were included in subject data listings.

Summaries included descriptive statistics for continuous variables (sample size, mean, and SD, median, minimum, and maximum) and for categorical variables (sample size, frequency, and percent).

Subject characteristics were summarized using the Randomized Analysis Set. No inferential statistics were planned.

9.7.1.9 Efficacy Analyses

9.7.1.9.1 Primary Analyses

The primary null hypothesis was that restoration of level of consciousness (defined as a return to GCS scores ≥ 13) of subjects with probable or definitive EHS was not different for subjects treated with SOC plus adjuvant Ryanodex therapy compared to subjects treated with SOC only. [REDACTED]

[REDACTED], the primary endpoint was the cumulative incidence of subjects achieving a GCS score ≥ 13 at or prior to 90 minutes post-randomization in the ITT Analysis Set.

The number and percentage of subjects who achieved a GCS score ≥ 13 at or prior to 90 minutes post-randomization were presented by treatment arm. A 2-sided 95% Wilson CI for each treatment group proportion and a 2-sided 95% Newcombe CI for the treatment difference were calculated. [REDACTED]

9.7.1.9.2 Sensitivity Analyses of the Primary Efficacy Variable

A series of horizontal black bars of varying lengths and positions on a white background. The bars are arranged in a descending order of length from top to bottom. The first bar is the longest and is positioned near the top. Subsequent bars are progressively shorter and are positioned further down the page. The bars are set against a white background with a thin black border around the entire image.

[figure not shown]

9.7.1.9.4 Exploratory Analyses

9.7.1.9.5 Subgroup Analyses

9.7.1.10 Safety

All safety variables were summarized using the Safety Analysis Set. All post-Baseline data were included.

9.7.1.10.1 Adverse Events

Adverse events were coded using the Medical Dictionary for Regulatory Activities (MedDRA) version 17.1. For each study treatment, numbers of events and incidence rates were tabulated by preferred term and system organ class. For each subject, an event that occurred one or more times after randomization contributed one observation to the numerator of the incidence rate. The denominator of the rate comprised all randomized subjects who received any treatment (i.e., the Safety Analysis Set). If the severity or seriousness of the AE changed, the overall severity or seriousness were the maximum severity or seriousness of the multiple occurrences.

Adverse events were listed for each subject and summarized by MedDRA system organ class and preferred term.

For this study, “treatment-emergent” AEs (TEAEs) were defined as AEs that started or worsened in severity on or after the initiation of first administered study treatment (SOC and Ryanodex, or SOC only). The incidence of all TEAEs, SAEs, related AEs, and related SAEs, was tabulated by treatment arm, overall and by maximum intensity. AEs leading to death, and AEs leading to withdrawal of subjects also were tabulated for each treatment group. Deaths due to any cause during the study were tabulated by treatment arm. Cases of rhabdomyolysis and ARF were identified at Baseline; any new cases that were identified post-Baseline or which worsened after the Baseline were reported as AEs. Post-Baseline severe respiratory distress or other medically important emergent events were reported as AEs. However, only AEs which occurred or worsened on or after the initiation of first administered study treatment were tabulated as TEAEs.

9.7.1.10.2 Clinical Laboratory Evaluations

9.7.1.10.3 Exploratory Safety Endpoints

[REDACTED]

[REDACTED]

[REDACTED]

[REDACTED]

9.7.1.10.4 Vital Signs Measurements, Physical Findings and Other Safety Evaluations

[REDACTED]

[REDACTED]

[REDACTED]

[REDACTED]

[REDACTED] [REDACTED]

[REDACTED]

[REDACTED]

[REDACTED]

2.0 SYNOPSIS

Name of Sponsor/Company: Eagle Pharmaceuticals, Inc.	Individual Study Table	(For National Authority Use only)
Name of Finished Product: Ryanodex® (dantrolene sodium) for injectable suspension		
Name of Active Ingredient: Dantrolene sodium		
Title of Study: Phase 2, Single-Site, Open-Label, Randomized, 2-Arm Parallel Study to Assess the Efficacy and Safety of Ryanodex® (EGL-4104) as Adjuvant Treatment in Subjects With Exertional Heat Stroke (EHS)		
Investigators: [REDACTED]		
Study Centers: The study was conducted at a single site with 3 additional satellite site locations in the region of Mekkah, Saudi Arabia, during the 2015 Hajj pilgrimage.		
Publication (Reference): None		
Study Period: 22 September 2015 (First Subject Enrolled) - 27 September 2015 (Last Subject Completed Treatment)	Phase of Development: 2	
Objectives: Primary : To evaluate the efficacy of Ryanodex for the treatment of EHS, administered as adjunctive treatment to current standard of care (SOC). Secondary : To evaluate the safety and tolerability of Ryanodex for the treatment of EHS by comparing the treatment groups for the incidence of treatment-emergent adverse events (TEAEs), physical and neurological examination findings, clinical laboratory test results, and vital signs.		
Methodology: [REDACTED]		

Name of Sponsor/Company:	Individual Study Table	(For National Authority Use only)
Eagle Pharmaceuticals, Inc.		
Name of Finished Product:		
Ryanodex® (dantrolene sodium) for injectable suspension		
Name of Active Ingredient:		
Dantrolene sodium		

Treatment Groups:

Upon admission to the emergency medical facility and following assessment of study inclusion and exclusion criteria, eligible subjects with probable or definitive EHS were randomized in a 1:1 ratio to one of the following treatment groups:

- Group A: Ryanodex, in addition to immediate implementation of SOC (body cooling and supportive measures)
- Group B: SOC only (body cooling and supportive measures) implemented immediately

Subjects randomized to Group A received an initial dose of Ryanodex (study drug) of 2 mg/kg administered as an IV bolus, in addition to SOC. If the subject did not show adequate clinical response between 30 and 90 minutes after the initial dose, a single repeat dosing of 2 mg/kg of study drug could be administered between 30 and 90 minutes following the initial dose.

Subjects who had received up to two 2-mg/kg (up to 4 mg/kg) IV doses of Ryanodex (Group A) during the Treatment Phase of the study could receive additional treatment with Ryanodex at a dose of 1 mg/kg as an IV bolus starting at 90 minutes following the initial dose and continuing every 6 hours for up to 24 hours under the following conditions:

1. If the subject had not achieved an adequate response (defined as rectal temperature $\leq 38.0^{\circ}\text{C}$ and Glasgow Coma Scale (GCS) score ≥ 13); or,
2. If the subject had achieved an adequate response (defined as rectal temperature $\leq 38.0^{\circ}\text{C}$ and GCS ≥ 13) but the symptoms began to reappear

Clinical assessments and symptoms leading to additional doses of study drug were to be clearly recorded. The total administered dose of Ryanodex in a [REDACTED] period was not to exceed [REDACTED]

Stopping the study drug:

If [REDACTED]

The study protocol included three phases (Screening/Randomization, Treatment Phase, and Follow-up

Name of Sponsor/Company: Eagle Pharmaceuticals, Inc.	Individual Study Table	(For National Authority Use only)
Name of Finished Product: Ryanodex® (dantrolene sodium) for injectable suspension		
Name of Active Ingredient: Dantrolene sodium Phase), plus a follow-up contact by telephone at approximately [REDACTED] days after the subject's discharge from the study.		
Number of Subjects (Planned and Analyzed): A total of 100 subjects (50 per arm) were initially planned to be randomized in the study. Due to unforeseen tragic events impacting the location of the study and enrollment plans, 40 subjects were screened to participate, and 34 subjects were randomized (6 subjects were screen failures). A total of 34 subjects were analyzed for efficacy and safety.		
Diagnosis and Main Criteria for Inclusion: Male or non-pregnant female subjects were entered into this study if they were diagnosed with probable or definitive EHS as evidenced by all of the following: 
 • A core body temperature obtained rectally of $\geq 40.0^{\circ}\text{C}$ (104.0°F) • In the judgment of the Investigator, the subject was likely 18 years of age or older, and not older than 45 years of age • Recent history or suspected recent history (prior 24 hours) of performing intense physical activity (exertional activity) • The subject had impaired consciousness level as evidenced by a GCS score < 13 • The subject had tachycardia (heart rate ≥ 100 beats per minute [bpm]). 		
Test Product, Dose and Mode of Administration, Batch Number: Ryanodex (dantrolene sodium) for injectable suspension; 250 mg/vial to be reconstituted with 5 mL of sterile water for injection (without a bacteriostatic agent) to yield a 50 mg/mL suspension; administered as a rapid IV push of 2.0 mg/kg or 1.0 mg/kg. Batch numbers of Ryanodex and sterile water for injection were [REDACTED] and [REDACTED], respectively.		
Duration of Treatment: Up to 72 hours, from Screening to medical discharge from the study.		
Reference Therapy: Standard of Care (SOC): All subjects in both treatment groups received SOC (efficient cooling and supportive measures).		
Criteria for Evaluation: Efficacy: The primary efficacy endpoint was cumulative incidence of subjects who had achieved a GCS score ≥ 13 at or prior to 90 minutes post-randomization. Secondary efficacy endpoints consisted of the following: 
 • Cumulative incidence of subjects who had achieved a GCS score ≥ 13 at planned time points • Changes from Baseline, and percent changes from Baseline in GCS scores over time • [REDACTED] • [REDACTED] 		

Name of Sponsor/Company: Eagle Pharmaceuticals, Inc.	Individual Study Table	(For National Authority Use only)
Name of Finished Product: Ryanodex® (dantrolene sodium) for injectable suspension		
Name of Active Ingredient: Dantrolene sodium		

Statistical Methods:
 
Sample Size: The planned sample size of 100 subjects (50 per group) was based on the predicted number of subjects who may be diagnosed with probable EHS during the 2015 Hajj. This sample size was planned to provide about [REDACTED] power to detect a difference between treatment means that was equivalent to 50% of the standard deviation (SD) (i.e., a moderate or medium-sized treatment effect) for any measure that had an approximately normal distribution, using a two-tailed Student t-test or F-test conducted at a significance level of 5%. Also, assuming that [REDACTED] of subjects who received SOC therapy with adjuvant Ryanodex treatment achieved a GCS ≥ 13 at 90 minutes post-randomization, compared to only [REDACTED] of subjects who received SOC only, the planned sample size would provide about [REDACTED] power for a 2-sided chi-square test to detect the difference between treatments at a significance level of [REDACTED].
 
Baseline: Baseline body temperature was the first rectal temperature $\geq 40.0^{\circ}\text{C}$ taken during the screening period.
 
[REDACTED]
 
[REDACTED]
		

Analysis sets: The Safety analysis set included all randomized subjects who received any study treatment (SOC only or SOC and Ryanodex). The Safety analysis set was used to analyze all safety endpoints using actual treatment received. The Intent-to-Treat (ITT) analysis set included all randomized subjects for whom SOC was initiated, and was used as the primary efficacy analysis set.
 
[REDACTED]
 
[REDACTED]
 
[REDACTED]
 
[REDACTED]
 
The ITT, [REDACTED] analysis sets were analyzed using planned treatment assignments. Classification of subjects with respect to the ITT, [REDACTED], and Safety analysis sets was conducted prior to the final database lock.
		

Efficacy Parameters:
 
The main focus of all efficacy analyses was to describe the course of subject recovery during the study and to obtain estimates of the treatment effect. Any observed significance levels ("p-values") that were reported were to be regarded as exploratory, descriptive statistics.
 
The primary null hypothesis was that restoration of level of consciousness (defined as a return to GCS scores ≥ 13) in subjects with probable or definitive EHS was not different for subjects treated with Ryanodex in addition to immediate implementation of SOC (body cooling and supportive measures), compared to subjects treated with SOC only (body cooling and supportive measures) implemented immediately.
 
[REDACTED]
 
[REDACTED] the primary endpoint was the cumulative incidence of subjects who had achieved a GCS score ≥ 13 prior to or at 90 minutes post-randomization in the ITT analysis set. The number and percentage of subjects who achieved a GCS score ≥ 13 are presented by treatment arm. A two-sided 95% Wilson confidence interval (CI) for each treatment group proportion and a two-sided 95% Newcombe CI for the treatment difference were calculated. The odds ratio and its two-sided 95% CI were also calculated and reported. The cumulative incidence of subjects who achieved a GCS score
		

Name of Sponsor/Company: Eagle Pharmaceuticals, Inc.	Individual Study Table	(For National Authority Use only)
Name of Finished Product: Ryanodex® (dantrolene sodium) for injectable suspension		
Name of Active Ingredient: Dantrolene sodium		

Secondary endpoints were analyzed for the ITT analysis set. Endpoints that consisted of actual values, changes from Baseline, or percent changes from Baseline were described by treatment group and planned time point, using basic descriptive statistics (N, mean, median, SD, two-sided 95% CI around the mean, minimum, maximum). Changes from Baseline in GCS and [REDACTED] were submitted to a repeated measures analysis employing a restricted maximum likelihood-based (REML), repeated-measure mixed model to obtain more precise estimates of treatment effect. SAS® Proc Mixed was used to perform the analysis. Each model included fixed terms for treatment group, time point, and treatment-by-time point interaction, with the Baseline value as covariate (as applicable), and subject as a random factor. An unstructured covariance matrix failed to converge when applied to pre-lock data, so a first-order autoregressive [AR (1)] covariance structure was used. An empirical ("sandwich") estimator for the variance-covariance matrix and the denominator degrees of freedom (DDFM) = BETWITHIN option for calculation of DDFM were used to take account of possible misspecification of the true covariance matrix. Predicted least square means, treatment differences between least square means, and two-sided 95% CI for the treatment differences are reported, overall and by planned time point, for all subjects in the analysis set.

Safety Parameters:

Incidence of TEAEs, serious adverse events (SAEs), related AEs, and related SAEs reported during the study was tabulated by treatment arm, overall and by maximum intensity. Deaths due to any cause during the study were tabulated by treatment arm. AEs were recorded from start of screening/randomization.

Name of Sponsor/Company: Eagle Pharmaceuticals, Inc.	Individual Study Table	(For National Authority Use only)
Name of Finished Product: Ryanodex® (dantrolene sodium) for injectable suspension		
Name of Active Ingredient: Dantrolene sodium		
Other: Demographics, subject disposition, dosing parameters, and [REDACTED] are summarized. [REDACTED]		

Name of Sponsor/Company: Eagle Pharmaceuticals, Inc.	Individual Study Table	(For National Authority Use only)
Name of Finished Product: Ryanodex® (dantrolene sodium) for injectable suspension		
Name of Active Ingredient: Dantrolene sodium		
Summary – Conclusions: Efficacy Results:		

 • A greater proportion of subjects treated with SOC and Ryanodex exhibited a clinically meaningful improvement in their neurological functioning (GCS ≥ 13) within 90 minutes (29.4%) and within 24 hours post-randomization (47.1%), compared to SOC only-treated subjects (11.8% and 23.5%, respectively) (ITT Analysis Set). • A greater proportion of subjects treated with SOC and Ryanodex achieved a clinically meaningful improvement (GCS score ≥ 13) in their neurological functioning as early as 45 minutes post-randomization compared to subjects treated with SOC only, and that difference in favor of the SOC and Ryanodex group remained unchanged at the end of the Treatment Phase (2 hours post-randomization) (ITT and mITT Analysis Sets). • The odds of achieving a GCS score ≥ 13 within 90 minutes post-randomization was about 3 times greater for subjects in the SOC and Ryanodex group than for subjects who received SOC only, and remained almost unchanged at or prior to 24 hours post-randomization (ITT Analysis Set). • Among fully evaluable subjects at Baseline, the odds of achieving a GCS score ≥ 13 within 90 minutes post-randomization was about 6 times greater in the SOC and Ryanodex group than for subjects who received SOC only (mITT Analysis Set). • Among fully evaluable subjects at Baseline, the mean change from Baseline in GCS score was higher in the SOC and Ryanodex group (3.1; $p=0.017$) compared with the SOC only group (1.1; $p=0.179$); the mean percent change from Baseline in GCS score was also higher in the SOC and Ryanodex group (55.6%; $p=0.073$) compared with the SOC only group (20.2%; $p=0.212$). In both cases, the within-group p-value clearly favors the SOC and Ryanodex group, compared with the SOC only group (mITT Analysis Set). • The proportion of subjects who achieved complete normalization in their level of consciousness (GCS score = 15) was greatest at 24 hours post-randomization and was greatest in the SOC and Ryanodex group (41.2%) than in the SOC only group (23.5%) (ITT Analysis Set). • Duration of SOC was substantially shorter in the SOC and Ryanodex group compared to the SOC only group (ITT Analysis Set). • The time to reach first rectal temperature $\leq 38^{\circ}\text{C}$ was similar in both treatment groups (ITT Analysis Set). • The median time to reach first rectal temperature $\leq 38^{\circ}\text{C}$ was shorter in the SOC and Ryanodex group (90.0 minutes) than in the SOC only group (103.0 minutes). In addition, the time at which at least 75% of the subjects had first rectal temperature $\leq 38^{\circ}\text{C}$ was also shorter in the SOC and Ryanodex group (125.0 minutes) than in the SOC only group (195.0 minutes) (mITT Analysis Set). • Overall mean cooling rates were similar in both treatment groups (ITT and mITT Analysis Sets). 
Subjects treated with Ryanodex in addition to SOC, exhibited greater clinically meaningful improvement in their neurological functioning compared to SOC only-treated subjects. The observed incremental improvement in neurologic functioning constitutes a clinically relevant benefit, known to be associated
		

Name of Sponsor/Company: Eagle Pharmaceuticals, Inc.	Individual Study Table	(For National Authority Use only)
Name of Finished Product: Ryanodex® (dantrolene sodium) for injectable suspension		
Name of Active Ingredient: Dantrolene sodium		
with lower risk of EHS-related complications, and decreased long-term morbidity and mortality.		

Safety Results:
 
 • Ryanodex was safe and well-tolerated by subjects in the SOC and Ryanodex group. • No new and/or unexpected safety signals were detected. • The overall incidence of TEAEs was similar in both groups. • No treatment-related TEAEs were reported. • No subjects withdrew due to TEAEs. • There were no clinically meaningful differences in laboratory abnormalities between the two treatment groups. • There were no clinically meaningful differences in vital signs, ECGs, ETCO₂, or oxygen saturation between the two treatment groups. • The safety profile of Ryanodex in this study population was consistent with the known and well-characterized safety profile in the currently approved indications. 		

Conclusion:
 
Overall, Ryanodex administered to EHS subjects was safe and well tolerated. The safety profile of Ryanodex in this severely ill population was consistent with its known and well-characterized safety profile in the currently approved indications.
 
Subjects treated with Ryanodex, in addition to SOC, exhibited greater clinically meaningful improvement in their neurological functioning compared to SOC only-treated subjects. The observed incremental improvement in neurologic functioning constitutes a clinically relevant benefit, known to be associated with lower risk of EHS-related complications, and decreased long-term morbidity and mortality.
 
The results of the study provide clinical evidence of the therapeutic benefit that Ryanodex may deliver to patients with EHS.

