9.7.1.3 Analysis Sets

The Enrolled Analysis Set included:

- Subjects who gave informed consent prior to participation.
- Subjects whose family member or authorized representative gave informed consent for the subject prior to participation.
- Subjects who entered the study under a waiver of informed consent.

Waiver of a subject’s informed consent occurred in the event the subject was unable to consent due to his/her medical status and a family member or authorized representative was not available at the time of hospital admission.

Once the study subject was capable of providing his/her own informed consent, then the subject was re-consented. If the subject was unwilling to provide consent at that time, the

subject was withdrawn from the study; and no further study procedures or testing were performed.

The Randomized Analysis Set contained all enrolled subjects who were randomized. For analyses and displays based on the Randomized Analysis Set, subjects were classified according to randomized treatment.

All efficacy was analyzed by planned treatment arm. Classification of subjects with respect to the ITT, [REDACTED] and Safety Analysis Sets was conducted prior to the final database lock.

9.7.1.4 *Missing Data*

Imputation of data in the mixed-model repeat measure (MMRM) analyses was not required, as the MMRM method provided appropriate weighting of the sample means based on the amount of data that each subject contributes.

Imputation of data was not required for any time-to-event analysis. Subjects were censored at the earlier of the 72 hours or discontinuation from the study.

Imputation of missing data was done on cooling rate (based on rectal temperature), using straight-line interpolation for non-monotonically missing data points only.

All other efficacy analyses methods consisted of descriptive statistics for observed cases.

9.7.1.5 *Adjustments for Covariates and Factors to be Included in Analyses*

Analysis of covariance (ANCOVA) models, including repeated-measure ANCOVA models, included the subject's respective Baseline value as a covariate.

Study site (location) was originally planned as a stratification factor in various analyses.

Study sites were [REDACTED]

[REDACTED] The specific analysis sections of the original SAP described how study site was to be used in the models (where applicable). Due to the actual study size, study site was deleted from all models and no tables or figures by study site were produced.

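### With 17 subjects per arm, a sandwich variance with no stated small-sample correction plus BETWITHIN degrees of freedom makes the mixed model's time-point 95% CIs about 5% to 8% too short

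*Combined protocol and SAP*

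**What the plan says.** The mixed model is described in the combined document, section 2.0 Synopsis, Statistical Methods (secondary endpoints). Changes from Baseline in GCS were fitted by REML in SAS Proc Mixed with treatment, time and their interaction, "with the Baseline value as covariate (as applicable), and subject as a random factor". An unstructured covariance did not converge on pre-lock data, so AR(1) was used. To guard against that structure being wrong, the plan chose a sandwich variance together with a df option; its wording is "for the variance-covariance matrix and the denominator degrees of freedom (DDFM) = BETWITHIN option for calculation of DDFM were used to take account", and the risk it names is a misspecified covariance. The output includes least-squares means and "two-sided 95% CI for the treatment differences are reported, overall and by planned time point".

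On sample size, the synopsis says "34 subjects were randomized (6 subjects were screen failures") and "A total of 34 subjects were analyzed for efficacy and safety". Subjects "were randomized in a 1:1 ratio to one of the following treatment groups".

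The SAP did adapt the models to the small sample in one respect (section 9.7.1.5): "Due to the actual study size, study site was deleted from all models". The visible text makes no small-sample change to the variance estimator or the degrees of freedom.

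**The concern.** Two features shorten the interval for the arm difference at a given time.

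1. **Sandwich variance.** The uncorrected estimator is built from fitted residuals, which are systematically smaller than the true errors. With 34 independent subjects the downward bias is not negligible.
2. **BETWITHIN.** This option gives effects that change within a subject, including treatment-by-time, the within-subject degrees of freedom. A difference between arms at one time compares 34 independent subjects, so it carries only about 34 - 3 = 31 df (two arm means and a baseline slope).

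The sandwich does protect against a wrong covariance structure. The larger df do not.

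The SAP (section 9.7.1.1) and the synopsis both make estimating the treatment effect the main aim and treat p-values as exploratory. The interval is therefore the main product of this model, and it shows more precision than 34 subjects support.

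**Working it through.** The documents give no standard error, df or interval width for this model, so there is no stated figure to reproduce.

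**Arm size.** The synopsis reports GCS recovery "within 90 minutes (29.4%) and within 24 hours post-randomization (47.1%), compared to SOC only-treated subjects (11.8% and 23.5%, respectively") in the ITT set, and 41.2% with GCS 15 on Ryanodex at 24 hours. With 17 per arm: 5/17 = 29.4%, 8/17 = 47.1%, 2/17 = 11.8%, 4/17 = 23.5%, 7/17 = 41.2%. Among arm sizes 10 to 24, only 17 fits all five. The implied odds ratios are (5/12)/(2/15) = 3.1 and (8/9)/(4/13) = 2.9, which agree with the synopsis figure of about 3.

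**Number of visits T.** This is not visible. Results are mentioned at 45 min, 90 min, 2 h and 24 h, so T = 4 and T = 8 are taken as assumptions.

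**Degrees of freedom under BETWITHIN** (complete data, baseline in the model):
- between-subject: 34 - 3 = 31
- within-subject: 34T - (2T + 1) - 31 = 32(T - 1), so 96 for T = 4 and 224 for T = 8

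**Standard error.** The ratio of the sandwich SE to the true SE is sqrt(32/34) = 0.970 without a covariate effect, and as low as sqrt(31/34) = 0.955 with the baseline covariate.

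**Closed form.** Shortfall = 1 - [t(0.975, within df) / t(0.975, between df)] × SE ratio. The true error rate is the two-sided tail of t(between df) beyond t(0.975, within df) × SE ratio.

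| T | t, within df | t, between df | SE ratio | Shortfall | Coverage | Error rate of a nominal 5% test |
|---|---|---|---|---|---|---|
| 4 | 1.985 (96) | 2.037 (32, no covariate) | 0.970 | 5.5% | 93.7% | 6.3% |
| 4 | 1.985 (96) | 2.040 (31) | 0.955 | 7.1% | 93.3% | 6.7% |
| 8 | 1.971 (224) | 2.037 (32, no covariate) | 0.970 | 6.1% | 93.5% | 6.5% |
| 8 | 1.971 (224) | 2.040 (31) | 0.955 | 7.7% | 93.1% | 6.9% |

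For T = 3 to 12 the shortfall runs from 4.9% to 7.9%.

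**Each part alone:**
- df only (31 against 96 or 224): 2.7% to 3.4% short, coverage 94.2% to 94.4%
- sandwich bias only: 3.0% to 4.5% short, coverage 93.9% to 94.3%

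**Simulation.** 20,000 null trials per setting, 17 per arm, complete data, REML, baseline covariate. Assumed visits were 45/90/120/1440 min or 30/45/60/90/120/240/720/1440 min. The working covariance was AR(1), with or without a random subject effect.

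| Truth | Time-point coverage as written |
|---|---|
| Correlation decaying with elapsed time | 92.7% to 93.5% |
| Exact AR(1) | 93.1% to 93.7% |
| SD doubling over follow-up | 93.0% to 93.5% |
| Bounded integer GCS, 3 to 15 | 92.9% to 93.6% |

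Over the first three rows the error rate is 100 - 93.7 = 6.3% to 100 - 92.7 = 7.3%. The shortfall persists when AR(1) is true, so neither covariance misspecification nor visit spacing causes it. A second simulation (3,000 to 6,000 replicates; T = 4, 6, 8, 10; AR(1) or compound-symmetric truth; some settings with unequal variance or 20% dropout) gave 92.8% to 93.6%.

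The overall contrast already gets about 31 df, so only the sandwich part applies. Its simulated coverage is 93.6% to 94.0%.

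**The case against.** - **Redaction.** Much of the SAP's secondary-analysis section (9.7.1.9.3) is blacked out, and more than half of the shortfall rests on no sandwich correction being stated. A correction could be there. This stands as a limit on the larger figure. The df choice is in plain text, and by itself it leaves the intervals 2.7% to 3.4% short.
- **No conclusion is shown to change.** The visible efficacy results quote proportions, odds ratios, medians and within-group changes, but no mixed-model arm difference by time. That is true. The plan nevertheless says those intervals are reported.
- **The analysis is secondary and exploratory.** This also stands, and it limits the importance of the point. An estimation-focused analysis still needs intervals close to their stated coverage.
- **The choices were meant to be protective.** The stated purpose was robustness to a wrong covariance, and the wish for better precision refers to the repeated-measures model as a whole. That is a fair reading of intent. It does not change the coverage, and the larger df add no robustness.
- **Visits are assumed.** They are, but the 5% to 8% range needs only about three, and four times are mentioned. With two visits it would be 3% to 5%.
- **Smaller analysis sets are speculative.** The synopsis places the secondary analyses in ITT. However, SAP section 9.7.1.9.3 names a second, redacted set for the GCS endpoints, so a smaller set is plausible. Its size is not known.

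**Conclusion.** The concern holds. As written, the ITT time-point CIs for the arm difference are about 5% to 8% too short and cover about 93% rather than 95%. A reported p of 0.05 corresponds to about 0.063 to 0.069. The overall contrast is affected less, and the primary Wilson and Newcombe intervals not at all.

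The arm size is firm. The number of visits and the absence of a sandwich correction are assumptions, the latter because of redaction. In any smaller set the shortfall grows: coverage is 91.5% to 92.3% at an assumed 10 per arm and 90.2% to 91.1% at an assumed 8.

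The error has a known direction and modest consequences. It is worth correcting because the correction is cheap.

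**What to change.** Keep the sandwich, but use a small-sample bias-corrected version and between-subject df (34 - 3 = 31 in ITT) for every treatment contrast, overall and by time point.

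- **Kauermann-Carroll with 31 df** restores simulated time-point coverage to 94.6% to 95.3%, and to 94.7% to 95.1% for bounded GCS scores.
- **Mancl-DeRouen with 31 df** gives 95.5% to 96.0%, slightly conservative. It reaches 96% to 97% at an assumed 8 to 10 per arm.
- **Check on the 90-minute contrast:** compare it with a single-time ANCOVA on baseline GCS with 31 df (simulated coverage 94.8% to 95.1%).
- **Sensitivity analysis only:** a model-based fit with a spatial power covariance, SP(POW), and Kenward-Roger df. It is unsafe as the main analysis if the variance changes over time.

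If the redacted text already states a corrected sandwich, only the df need to change.

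The study is complete, so this should be a documented re-run shown beside the existing intervals, not a replacement for them. It costs a few lines of code and a paragraph describing the method. Time-point CIs widen by about 7% to 8% with Kauermann-Carroll, or 12% to 13% with Mancl-DeRouen.
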